- Government agencies and public health authorities, such as the Food and Drug Administration (FDA) and the Department of Health and Human Services (DHHS)

PROVISIONS TO PROTECT THE PRIVACY INTERESTS OF PARTICIPANTS Steps taken to protect privacy of participants:

The participants will only provide personal information to the study personnel listed on the IRB. All data is obtained specifically and solely for research purposes. The data is made unidentifiable by using anonymous participant codes to minimize the risk to the participants' privacy. Behavioral and functional data will be the only form of research material obtained from individually identifiable living human participants. Human participant personal information (name, contact information) and medical information necessary to the study (age, sex, possible diagnoses, medications) will be taken during recruitment. All recordings are kept in a secure computer, non-accessible to other investigators other than the ones listed on the protocol. All information regarding experimental participants, including consent forms, will be kept in a locked file cabinet. There will not be any type of collection of sensitive data, such as sexual, criminal, or illegal behavior.

Steps taken to ensure participant comfort:

To ensure that participants feel at ease, the purpose of the study in addition to the procedures will be clearly described. At the beginning of each session, the relevant procedures are reviewed with the participant. Throughout the study, there will be open communication between the participant and the research staff, and the study will be stopped should the participant feel uncomfortable with any of the questions or procedures that are part of the protocol.

Research staff permissions:

All study staff are CITI certified and all information and records are in compliance with HIPAA rules.

COMPENSATION FOR RESEARCH-RELATED INJURY

If the participant gets an injury or illness as a result of study, the participant is required to promptly notify the PI or research personnel of the study about the illness or injury. The hospital [Researchers, Shirley Ryan AbilityLab, Northwestern University, and all affiliated clinical sites] will not pay for medical care required because of a bad outcome resulting from participation in this research study. However, this does not keep participant from seeking to be paid back for care required because of a bad outcome.

ECONOMIC BURDEN TO PARTICIPANTS

There is no anticipated economic burden to the participants since they will be inpatients and the study will occur in the same building. Participants will not receive compensation for their participation in this study.

CONSENT PROCESS

Prior to enrollment into the study, the participant will be provided an explanation of the study and the opportunity to review the consent form. Once this is complete and research personnel ensures the participant understands the implications of participating in this study, informed consent will be obtained from the participant with their signature on the IRB-approved consent form. In order to participate in the study, the consent form must be signed and dated by the

IRB Project #: STU00213155, Medical Clearance Form (v01) 08/05/2020 Page 13 of 17 Principal Investigator: [name]

HRP-593 / v03152019

participant and the research personnel who completed the consenting discussion. If any changes to the protocol are made, participants will be consented with an updated consent form.

Adults able to consent:

For participants with stroke, informed consent will be obtained by the PI or any trained licensed physical therapist prior to completion of study protocol. We will ensure the participant understands the purpose of the study, the procedures, risks and benefits, and rights as a research participant, and he/she can provide informed consent. Participants able to make their own decisions regarding research participation will be allowed to discuss with other appropriate parties prior to giving informed consent. Participants will not be openly encouraged to participate in the research or told that there is any expected benefit from the experimental interventions during participation. Participants will have access to research staff to assist with any questions or concerns until understanding is achieved to the judgment of the individual asking the question. If a participant refuses participation, no further contact will be made.

Adults able to consent who have communication deficits:

For participants who demonstrate communication deficits (i.e. aphasia) but who are deemed safe to consent by their supervising medical and therapy team, we will provide necessary supportive communication strategies to ensure proper understanding of the consent process prior to obtaining consent.

Adults unable to consent:

For those deemed unable to consent by their supervising medical and therapy team as a result of their stroke, we will obtain informed consent from their POA. We will ensure the POA understands the purpose of the study, the procedures, risks and benefits, and the participant's rights before providing informed consent on behalf of the participant.

Process to document consent in writing:

Informed consent will take place at Shirley Ryan AbilityLab on the inpatient floors with authorized study personnel.

Trained research personnel will guide the participant through consenting process. The participant will be given detailed explanation of the purpose, timeline, commitment, procedures, data handling, privacy, and confidentiality of information pertaining to the study.

For all participants, we will obtain written consent as usual. The signed consent form will be stored in a locked cabinet for the duration of the study. Our consent document has been uploaded to the eIRB folder.

NON-ENGLISH SPEAKING PARTICIPANTS

The study will only recruit participants who are fluent in English because all tests and instructions are administered in English.

PROTECTED HEALTH INFORMATION (PHI AND HIPAA)

Participant records will be kept completely confidential. Every possible precaution will be taken to protect the privacy interests of participants. Participation in this study is completely voluntary. Trained research personnel will explain the purpose of the study, the intended use of a participant's medical information, and the precautions taken to keep the study information and data confidential. Data will be collected and kept confidential and compliant with HIPAA standards.

IRB Project #: STU00213155, Medical Clearance Form (v01) 08/05/2020 Page 14 of 17 Principal Investigator: [name] HRP-593 / v03152019 Participants will be assigned an alphabetical or numerical study identification number. Identifying data will be kept in locked cabinets and password protected servers completely separate from de-identified data. Research data will be de-identified and stored in locked cabinets in the lab accessible only to authorized research personnel. Electronic data will be deidentified and kept on secure, password protected servers at the Shirley Ryan AbilityLab. Only authorized research staff will be able to access any of the formerly mentioned data. Deidentified data will be kept indefinitely.

Study documentation will be collected and stored and kept confidential and compliant with HIPAA requirements.

All personal information (names, addresses, email or phone numbers, etc.) gathered for this study that can identify participants will be kept secure to protect their privacy and will never be shared with any person or entity at any time. Data collected during the study and shared with others will reference participants only by an alphanumeric code. The "master list" linking personal information to the alphanumeric code will not be shared and will be kept in a secure location.

QUALIFICATIONS TO CONDUCT RESEARCH AND RESOURCES AVAILABLE Describe other resources available to conduct the research:

The Shirley Ryan AbilityLab services the stroke poption at a rate of approximately 300 new patients per year. The Shirley Ryan AbilityLab is a research hospital that maintains a research registry (greater than 750 participants). We will recruit inpatients to meet our enrollment goal and perform all research on site at the flagship hospital. The study team members are all employees of the Shirley Ryan AbilityLab. They are familiar with the study site and are experienced with the study population. There will be medical resources including a resident on call and nursing staff available 24 hours a day if needed in case of an emergency.

All study team members will be trained on the study protocol and procedures and have already been trained on how to safely administer all functional outcomes using standardized methods. The research staff consists of clinical researchers and licensed physical therapists trained in the safe use of therapeutic equipment, including the harness system used for locomotor training in the overground gait track and over all treadmills, gait belt use for assessments, and emergency management of the EksoNR exoskeleton. In addition, three therapists within the Legs + Walking team have completed both Part 1 and Part 2 of the EksoNR standardized training program. Experienced physical therapists will lead the assessment and treatment sessions. Finally, all research and therapy staff members have been CITI-certified and have Basic Life Support (BLS) training.

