Individuals with stroke admitted as inpatients to the Shirley Ryan AbilityLab will be asked to potentially enroll in the study. A thorough review of the participant's medical history will be completed by licensed physical therapists, and medical clearance will be obtained from the individual's medical team. The study coordinators will assess eligibility based on inclusion criteria, obtain informed consent, and answer any questions from the participant and/or his/her power of attorney (POA). If the participant is deemed unable to consent by the primary medical team, consent will be obtained from the individual's power of attorney (POA). Following informed consent, participants will undergo a physical evaluation and screening exam by a licensed physical therapist. Once they are enrolled, baseline outcome measures will be assessed by a physical therapist [See Clinical Assessments section].

If a participant is placed in the intervention group receiving gait training via the EksoNR exoskeleton, additional steps will be taken during baseline assessments to ensure the participant is appropriate for use of the EksoNR. These measures include upper and lower extremity range of motion, upper and lower extremity strength, spasticity, transfer status, skin integrity, and then three specific body measurements to assist with setting up the EksoNR exoskeleton. The three body measurements include hip width measured in sitting, upper leg lengths measured supine on a mat table, and lower leg lengths measured sitting on the edge of the mat table with feet supported on a step. Measurements are compared bilaterally and then converted to EksoNR values using a chart from Ekso Bionics (See User Manual). All assessments will be completed by a trained physical therapist to ensure standardization and safety of the participant.

Procedures during treatment:

After the baseline testing is completed, participants will complete between 9-24 training sessions dependent on their length of stay. These training sessions will occur in the inpatient Legs + Walking Lab with a licensed physical therapist and will last up to 90 minutes. Each session will be customized based on the participant's functional capacity with the goal of maximizing stepping practice.

Body-weight-supported treadmill + overground gait training group:

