We anticipate it will take each participant up to eight weeks to complete the study protocol. Clinical assessments will be performed at baseline and once weekly for up to eight assessment sessions or until the participant is discharged. The intervention will be delivered three times weekly up to 24 sessions or until the participant is discharged. In total, each individual will participate in 13-34 sessions [Refer to Figure 3]. We anticipate a 12-month period to enroll all inpatient participants.

Type of Session	# of Sessions	Time Required for Each Session
Enrollment/ Baseline Clinical Assessment/ Baseline Measurements	1-2	60-120 minutes
Weekly Clinical Assessments	3-8	60-90 minutes
Training Protocol	9-24	60-90 minutes

Figure 3. Summary of sessions.

INCLUSION AND EXCLUSION CRITERIA Inclusion Criteria:

- Age 18-80 years old
- Unilateral, supratentorial ischemic or hemorrhagic stroke within the past six months
- Medical clearance from primary medical team (signed Medical Clearance form)
- CPB as determined by a score of >0 on the Scale for Contraversive Pushing
- Adequate cognitive function as determined by the NIH scale: score ≤1 on question 1b and score =0 on question 1c
- Informed consent provided by participant or POA
- English speaking

Exclusion Criteria:

- Severe aphasia limiting ability to express needs or discomfort verbally or nonverbally
- Severe behavioral neglect as determined by a score of ≥ 21 on Catherine Bergego Scale (CBS) via the Kessler Foundation-Neglect Assessment Process (KF-NAP)¹⁶
- History of prior stroke
- Concurrent neurologic condition (i.e PD, TBI, MS, etc.)
- History of peripheral nerve injury
- Joint contracture or significant spasticity in the lower limbs (Modified Ashworth Scale \geq 3)
- Severe knee, hip, or ankle osteoarthritis
- Severe osteoporosis as indicated by physician medical clearance
- Open wounds on surfaces in contact with exoskeleton or harness
- Unstable spine or unhealed fractures
- Weight bearing precautions
- Unresolved deep vein thrombosis (DVT)
- Concurrent participation in other lower limb research studies that according to the PI is likely to affect study outcome or confound results
- Pregnancy

EksoNR Exclusion Criteria¹⁷:

- Weight >220 lbs (100 kg)
- Height below 60 inches or above 76 inches
- Standing hip width of approximately 18 inches or more
- Joint contractures or range of motion deficits that limit normal range of motion during ambulation
 - Knee flexion contracture greater than 12°

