 - Hip flexion contracture greater than 17°
 - Inability to achieve 0° neutral ankle dorsiflexion with knee flexion up to 12°
 - Bilateral hip flexion less than 110°
- Leg length discrepancy
 - Greater than 0.5 in. (1.27 cm) for upper legs
 - Greater than 0.75 in. (1.91 cm) for lower legs
- Active heterotopic ossification
- Significant spasticity in the lower limbs (Modified Ashworth Scale ≥3)
- High anxiety or claustrophobia
- Clostridium difficile or other gastrointestinal isolation precautions
- Colostomy
- Uncontrolled autonomic dysreflexia
- Lower limb prosthesis

VULNERABLE POPULATIONS

We will recruit participants with communication deficits (i.e. aphasia) as a result of their stroke who are deemed safe to consent by their supervising medical and therapy team. For these participants, we will provide the necessary supported communication strategies to ensure the proper understanding of the experimental protocol and consent process prior to obtaining consent.

For those deemed unable to consent by their supervising medical and therapy team as a result of their stroke, we will obtain informed consent from their POA. We will ensure the POA understands the purpose of the study, the procedures, risks and benefits, and the participant's rights before providing informed consent on behalf of the participant.

PARTICIPANT POPULATION(S)

Accrual	Category/Group:	Consented:	Enrolled:
Number:	(Adults/Children	Maximum Number to be	Number to Complete
	Special/Vulnerable	Consented or	the Study or Needed
	Populations)	Reviewed/Collected/Screened	to Address the
			Research Question
Local	Adults with stroke + CPB	45	30
Study-wide			
Total:		45	30

RECRUITMENT METHODS

This study will involve recruitment of individuals with stroke from the inpatient units at the Shirley Ryan AbilityLab. Clinicians at this location will be informed of the inclusion and exclusion criteria for this study in order to refer appropriate participants to the study coordinators. Information regarding this study will be posted on the Shirley Ryan AbilityLab webpage detailing available research studies. Authorized research personnel will identify and screen potential research participants based on inclusion and exclusion criteria using the Cerner application. After identification of participants based on inclusion and exclusion criteria, a verbal permission from the participant will be obtained to request medical clearance from their physician.

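### The EksoNR suitability check is described only after placement in that group, and no text clearly applies the EksoNR exclusions to treadmill candidates, so the group comparison is open to selection bias of unstated size and direction

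*Protocol*

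**What the plan says.** Under Procedures Involved (Screening, enrollment, and baseline procedures), coordinators assess eligibility and obtain consent, and a physical therapist then carries out an evaluation and screening exam whose content is not described. The device check follows: "If a participant is placed in the intervention group receiving gait training via the EksoNR exoskeleton, additional steps will be taken during baseline assessments". It covers range of motion, strength, spasticity, transfers, skin and "three specific body measurements to assist with setting up the EksoNR exoskeleton". The first two of these measurements are "hip width measured in sitting, upper leg lengths measured supine on a mat table"; the third is lower leg length.

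Inclusion and Exclusion Criteria has a general exclusion list and, after it, a list headed for the EksoNR alone. The second list includes a weight limit of 220 lb (100 kg), height outside 60-76 inches, "Standing hip width of approximately 18 inches or more", "Leg length discrepancy", "High anxiety or claustrophobia", heterotopic ossification, gastrointestinal isolation, colostomy, autonomic dysreflexia and lower limb prosthesis. The general list already contains "Joint contracture or significant spasticity in the lower limbs", with the same Modified Ashworth threshold of 3 that the EksoNR list repeats.

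Recruitment Methods has staff screen candidates in the records system against the inclusion and exclusion criteria, without saying whether this includes the EksoNR list. Data Collection and Analysis plans a comparison of the two groups leading to conclusions on efficacy. The protocol does not state how participants are placed in a group, or what happens to someone who fails the EksoNR check.

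**The concern.** A comparison of two treatments needs both groups to come from the same eligible population. If a set of physical and medical limits binds one group only, the groups can differ before the first session, and part of any difference in outcome may come from who was allowed in. A larger sample would not remove this.

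Therapist burden is one plausible route. Measuring it is a stated objective, the Background expects the EksoNR to reduce it, and therapist heart rate, exertion and pain are recorded every session. A weight ceiling in the EksoNR group alone could make that device look less burdensome because its participants are lighter. Body-weight support on the treadmill may offset part of this, although staff there still help to advance the limbs, so the direction is plausible rather than certain. For pushing, balance and gait, the protocol gives no basis for a direction.

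**Working it through.** **1. Which reading the text supports.**
- The suitability step is conditional on placement in the EksoNR group.
- The EksoNR list has its own heading and repeats the Ashworth threshold from the general list. That repetition would be redundant if both lists applied to everyone.
- The general list has an item on open wounds that names both exoskeleton and harness, so it is written to cover both devices where that is meant.

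Together these make it natural to read the second list as binding the EksoNR group only. This is an inference; no sentence says so.

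**2. Which items create the asymmetry.** Spasticity is excluded in everyone. Contracture overlaps in part, because the EksoNR list adds specific joint limits. Range of motion, muscle strength and the Ashworth scale are assessed in all participants. What remains is weight, height, standing hip width, leg-length discrepancy and the medical items. Of these, only leg lengths, and a hip width taken in sitting, are shown to be measured after placement. The assessments listed for all participants contain no weight, height, hip width or leg length. Medical history may be collected and could supply weight and height.

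**3. Illustrative size.** There is no protocol figure to reproduce, and every input here is assumed: equal placement that ignores suitability, a fraction f who fail the EksoNR-only criteria, and an outcome in those people that differs by d SD.

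- Failures dropped from the EksoNR group: the treadmill group contains a share f of such people and the EksoNR group none, so bias = f × d.
- Failures moved to the treadmill: of n(1 + f) people there, 2fn would fail, so bias = [2f/(1 + f)] × d.
- Placement that simply follows suitability, with everyone who fails in one group and everyone who passes in the other: bias = d.

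| f | d | Dropped (SD) | Moved (SD) |
|---|---|---|---|
| 0.1 | 0.5 | 0.05 | 0.09 |
| 0.2 | 0.5 | 0.10 | 0.17 |
| 0.3 | 0.5 | 0.15 | 0.23 |
| 0.3 | 0.8 | 0.24 | 0.37 |

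At d = 0 every entry is nil.

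**4. Against sampling error (dropped case).** SE = √[1/(n(1 − f)) + 1/n], with n placed per group.
- n = 15, d = 0.5: SE = 0.375, 0.387, 0.402 for f = 0.1, 0.2, 0.3; bias/SE = 0.13, 0.26, 0.37.
- n = 10, d = 0.5: SE = 0.459, 0.474, 0.493; bias/SE = 0.11, 0.21, 0.30.
- n = 15, f = 0.3, d = 0.8: 0.24/0.402 = 0.60.

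**5. Chance that the unhandled case arises.** P(at least one failure among n placed in the EksoNR group) = 1 − (1 − f)^n. At f = 0.1 this is 41% for n = 5, 65% for n = 10 and 79% for n = 15. At f = 0.3 it is 83%, 97% and 99.5%.

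**6. Weight limit alone.** Assume weight is roughly normal with a share p above 100 kg. The treadmill mean exceeds the EksoNR mean by φ(z)/(1 − p) SD of body weight, where z = Φ⁻¹(1 − p). For p = 0.05, 0.10, 0.20 this is 0.11, 0.20, 0.35. With an assumed weight-burden correlation of 0.3, burden shifts by 0.03, 0.06, 0.11 SD.

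**The case against.** The EksoNR list sits inside the general criteria section, and Recruitment Methods screens candidates on inclusion and exclusion criteria before group placement is mentioned. Weight, height, colostomy and similar items can be read from a chart, and the post-consent screening exam could cover others. This stands to the extent that one cannot say the list is definitely withheld from treadmill candidates. The screen is ambiguous, and the ambiguity itself needs correcting.

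A reader might infer that people who fail the check are withdrawn. Withdrawal of Participants covers safety concerns and inability to follow the protocol, and does not mention failing the device check. Dropping, moving and replacing are all open.

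A reader might also infer that an analysis plan could never repair this. If weight and height are collected, the burden route could be handled by adjustment or restriction. Leg lengths and standing hip width are not described for treadmill participants, so eligibility for both groups could not be fully rebuilt, but no route from those two items to an outcome is shown.

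The sitting hip width is taken for set-up and the standing one is an exclusion, so this is not a strict contradiction. What stands is that the described step does not measure the excluded quantity.

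Finally, common eligibility alone does not make the groups comparable while placement is undefined. That is correct and limits what the remedy achieves.

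**Conclusion.** The point holds in a limited form. The suitability check is described only for people already in the EksoNR group, the separate list is not clearly applied to treadmill candidates, and on the natural reading the groups come from different eligible populations. Eligibility and its timing belong in the protocol, so this cannot be left to an analysis plan.

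The size and direction of the bias are not fixed by the document. A reader might take the figures above to show that the bias is modest, or always well below sampling error. They do not. Every input is assumed, the ratio reaches 0.60 of a standard error within the range examined, and the dropped and moved formulas do not apply if placement is by judgement. Nor does the protocol show that the bias is large: if those who fail have the same outcomes as others, it is nil. This should be fixed before enrolment; confidence is medium, because non-application to the treadmill group is inferred.

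**What to change.** Apply the existing EksoNR exclusion list to every candidate before group placement, and place only people eligible for both groups. If that pool is too small, record EksoNR eligibility in everyone before placement, including weight, height, leg lengths and standing hip width. Then make the primary between-group comparison among those eligible for both, and report the other treadmill participants separately. For analysis, keep anyone found unsuitable after placement in the group as placed. Reconcile the sitting hip width in the baseline procedures with the standing hip width in the criteria.

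The cost is protocol wording, a checklist, a few body measurements and a somewhat smaller comparable pool. The protocol's figures of about 300 new stroke patients a year, 12-18% with pushing behaviour and 12 months of enrolment give 300 × 0.12 to 0.18 = 36-54. If general exclusions and refusals remove 30% or 50% (assumed), 25-38 or 18-27 remain. Removing a further 20% (assumed) leaves 20-30 or 14-22. That is compatible with the 5-10 per group in the Background but may miss the 30 in the accrual table, a target already out of reach at 50% loss without the change. The second option leaves enrolment unchanged, though the compared set still shrinks.

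Either option removes the eligibility imbalance. Neither replaces a stated placement method, which the protocol still needs.
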